### **Study objectives:**

**Primary objective:** Demonstrate that remote tDCS sessions applied by a caregiver are feasible, complied and adhered to, and are safe in individuals with severe depression

**Secondary objective:** Gather pilot data on the potential of home-based tDCS to induce clinically meaningful improvements in the severity of depression in individuals who would otherwise be offered rTMS or ECT treatment.

The ultimate goal of this work is to prepare the path for a subsequent randomized clinical trial to assess the antidepressant therapeutic efficacy of home-based tDCS. We thus propose a study of tele-health supervised, caregiver-delivered, home-based tDCS for antidepressant treatment of patients with a medication-resistant depression episode of uni- or bi-polar Major Depression who would otherwise qualify for rTMS or ECT.

Specifically, in the present protocol we seek to offer participation to:

- Patients with medication-resistant MDD who have undergone rTMS or ECT and responded to it but whose benefit has lapsed, and they need repeat a rTMS or ECT course that they cannot access
- Patients with medication-resistant MDD who are undergoing rTMS or ECT and responding, but cannot continue to get the rTMS or ECT course due to COVID-19 pandemic-related regulations or other access concerns
- Patients with medication-resistant MDD who are referred to rTMS or ECT and are found well qualified but cannot access rTMS or ECT due to COVID-19 pandemic-related regulations or other access concerns.

The benefits of this project address a present need due to the COVID-19 pandemic, but also go beyond the present situation and address a larger, pre-existing need.

Across all these potential groups of participants, prospective participants will:

1. Need to have a primary psychiatrist who agrees to their participation in the study and is willing to continue to follow the patient and work collaboratively with the study team
2. Need to be assessed by their primary psychiatrist to be stable enough to be able to remain at home and participate in the present study without undue risk to their safety
3. Need to be living with an adult willing and capable to provide oversight and learn to deliver the home-based tDCS
4. Have the capability to connect with the study team for daily supervision of the intervention sessions and close safety monitoring, and be willing to commit to doing so

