## Home-use device and training to caregivers

Alonzo et al. (2019) used a tDCS device that required the placement of individual, large sponge electrodes onto the scalp in positions defined by the 10-20 EEG electrode placements (F3 and F8). The large sponge electrodes needed to be held in place by elastic bands. The procedure posed substantial challenges and precluded some caregivers from achieving appropriate level of competency. In addition, the interface with a programmable device for specification of stimulation parameters was challenging and again represented a hurdle for some patient-caregiver pairs.

Neuroelectrics has developed a system for home-based tDCS that effectively overcomes these challenges and is being used in several studies, e.g. Garcia-Lorrea 2019 (<https://clinicaltrials.gov/ct2/show/NCT02346396>). The Starstim Home Kit® (Neuroelectrics Corp) is commercially available and approved in Canada for use in treating chronic pain, depression and addictive disorders. It utilizes the company's industry leading Starstim system, with additional features that enable researchers and clinicians to "prescribe" and monitor home-based tDCS to end users. Briefly, the Starstim system resembles a swimming cap that fits loosely on the head, but with small electrodes that lie on the scalp and deliver low-level electrical currents to targeted brain regions. Within the Home Kit, the relevant electrode positions are marked on the headcap with different colors and numbers, and the corresponding electrode leads (cables) from the tDCS device are marked with the same colors and numbers. This ensures that the user places the electrodes in the correct position and secures the correct lead to each electrode. The Home Kit also utilizes a tablet that provides the user with step-by-step instructions to set up the Starstim device, check electrode impedance, and record side effects. The user may also videoconference with remote staff in real-time. The researcher uses Neuroelectrics online Portal (NE Portal) to remotely schedule sessions and monitor in real-time specific treatment events to ensure safety.

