At the Marcus Institute we have developed a training and in-home supervision program to accompany the Starstim Home Kit and have established its feasibility in two ongoing studies (one focused on gait and balance and the other on episodic memory in dementia). In these studies, to date we have completed the assessments of eight participant 'pairs;' that is, an individual to receive tDCS along with a family member, friend, or care-giver willing and able to administer tDCS. Each potential administrator was initially screened to ensure that they would be available throughout the intervention period and to ensure they had at least minimal computer proficiency. They were then trained by staff to administer tDCS to the study participant and did so under the supervision of staff until they self-reported comfort in the process and were deemed proficient as determined with a custom-developed checklist. For all eight participant-pairs, the administrators, who ranged in age from 44 to 87, achieved proficiency by the third session of tDCS. All but one pair completed at least eight sessions of the 10-session intervention. No adverse events were reported. Transient skin redness and tingling sensations under the electrode were the only reported side effects and the frequency and severity of these side effects were similar to that reported in published staff-administered interventions. Upon exit interview, all administrators—and the participants who received the stimulation—stated that the Home Kit and training materials were easy to use, that

they were satisfied with the experience and training they received, and that they would be willing to use to system again in the future.

The above studies utilize in-person training methods until the participant administrator achieves proficiency. For the current proposal, a video telemedicine-based training program is available to ensure minimal staff-participant contact. Moreover, a pre-configured Starstim system will be shipped directly to the participants with all the required supplies and documentation.

Eligibility Criteria: Patients meeting one of the following criteria may be eligible to participate in this study.

1. Patients with medication-resistant MDD who have undergone rTMS or ECT and responded to it but whose benefit has lapsed, and they need repeat a rTMS or ECT course that they cannot access

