### Visits (All visits will be conducted remotely)

For this study, participant caregiver administrators will be provided remote step-by-step training to administer the tDCS sessions to the participants with MDD. Participant caregiver-administrators will be directly supervised remotely, until they demonstrate proficiency, without coaching by the study team. We have developed a step by step training manual, and have successfully trained older adult caregivers to administer the tDCS.

Visit	Purpose	Procedures	Study personnel	Duration	Location
Pre-ICF	Advance review	Informed consent pre-review by potential participants	RA will send	As needed for review	Mailed/emailed to P
Visit 1	Remote screen and assessment visit	Informed consent [ P with MDD ] Mental Health/Medical health history; medications; Cognitive Assessment; Interview with study psychiatrist [ Participant caregiver-administrators ] Health history; computer proficiency questionnaire [ Both participants ] tDCS overview and training	Study research assistant; Study psychiatrist	~ 1 hour	Remote
Home tDCS administration Treatment period – Daily tDCS sessions over 4 weeks *Participant ratings of suicidality will be completed each day, and responses will be monitored and immediately be reviewed in real time by the study RA and study psychiatrist. Any changes from baseline will result in an immediate contact to the participant by the study psychiatrist.					
Week (Wk)1; Day (D) 1	Home-based tDCS	At-home tDCS equipment set-up; tDCS administration by caregiver-administrator with step-by- step remote training by study staff Daily diary	Study research assistant	1 hour total (tDCS session=30 mins)	Video conference
Wk1, tDCS session	Home-based tDCS once a day	tDCS admin by the caregiver-administrator with remote staff oversight and coaching Daily	Study research assistant	1 hour total (tDCS session=30)	Video conference

D 2-4		diary		mins)	
Wk 1, tDCS session D 5	Home-based tDCS	tDCS admin by the caregiver-administrator with remote staff oversight and coaching; Staff administered skills test for caregiver-administrators Daily diary	Study research assistant	1 hour total (tDCS session=30 mins)	Video conference
Wk 1-4; D6-28	Home-based tDCS once a day	The caregiver-administrator will administer the in-home tDCS session with remote staff monitoring and video conferencing if necessary Daily diary	Study research assistant	1 hour	Participant's Home

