## Statistical Methods and Analysis

### *Primary*

Feasibility and tolerability/safety will be evaluated using home-based data as it is collected by reported number of aborted sessions.

The *primary outcome* will be change in the observer rated MADRS score from baseline to the 1-month follow-up.

Clinical response is defined as  $\geq 50\%$  improvement in MADRS score from baseline to the 1-month follow-up. Remission is defined as a MADRS score  $\leq 10$ .

The *secondary outcome* measures will include the participant-rated Quick Inventory of Depressive Symptomatology (QIDS-SR) (Rush et al., 2003) and the Quality of Life Enjoyment and Satisfaction Questionnaire Short Form (Q-LES-Q-SF) (Endicott et al., 1993), both administered at the same time points as the MADRS. A computer-based cognitive test battery, CogState (<https://www.cogstate.com>), will provide an additional safety outcome measure. This battery includes tests designed to assess verbal learning and memory (International Shopping List Task), attention and psychomotor function (Detection Task), visual attention (Identification Task), visual learning and memory (One Card Learning Task), working memory (Two Back Task), and executive function (Set Shifting Task).

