## Data storage and confidentiality

Data will be kept on a secure, password protected HSL server in a REDCap Database. Only study members at the HSL site will have access to the HSL REDCap database. All hard copy forms will be kept in a locked filing cabinet that only study members will be able to access. All policies and procedures of Hebrew Senior Life with regard to data storage will be followed.

Data collected will be stripped of identifiers. Data will be assigned a code number and no personal identifying information will be associated with study data in any format, including electronically. Only the investigators will know information about a particular subject. Identifying information about a subject will be stored in locked computer files and cabinets and will not be used during the discussion, presentation, or publication of any research data.

Results of the study will be shared with the participant's psychiatrist if the participant has given study staff permission to do so.

List of Assessments and forms:

[Sociodemographic form\\_2 8619.docx](#)

[Medical History Questionnaire\\_1 92718.docx](#)

[Medication Review Form\\_1 92818.docx](#)

[Q\\_LES\\_Q\\_SF.docx](#)

[QIDS\\_SR.pdf](#)

[Suicide Risk Assessment Protocol.pdf](#)

[tDCS Eligibility Questionnaire\\_41220.docx](#)

[001\\_Coverletter-Depression.docx](#)

[002\\_HOME\\_tDCS\\_MDD\\_STUDY\\_04\\_07\\_2020\\_v1.0.docx](#)

[003\\_Annex I- Safety Analysis of tDCS in Craniotomies.docx](#)

[004\\_Annex II-Home based tDCS for MDD Training Manual.docx](#)

[005\\_Annex III-Caregiver tDCS Competency Checklist.docx](#)

[006\\_Annex IV-SPR0157\\_IDLPFC\\_DepressionHome.pdf](#)

[Assessment of Understanding Protocol\\_mdd.docx](#)

[tDCS Side Effects Questionnaire\\_mdd.docx](#)

[FDA IDE approval letter G160208-S003.Letter.NEWS.APPR \(002\).pdf](#)

[Evaluation Form Home based tDCS in MDD\\_Caregiver-administrator.docx](#)

[Revised CPQ\\_v1.docx](#)

[Proxy and Medical care Info.792019.docx](#)

[Evaluation Form Home based tDCS in MDD\\_v2PMDD.docx](#)

[PhoneScreenQuestionnaire\\_Caregiver-administrator\\_clean.docx](#)

[PhoneScreenQuestionnaire\\_PMDD\\_v2\\_5420.docx](#)

[tDCS Eligibility Questionnaire\\_41220.docx](#)

[Home based tDCS MDD Training Manual v5 5120.docx](#)

[MADRS.pdf](#)

[Evaluation Form Home based tDCS in MDD\\_v2PMDD.docx](#)

[Caregiver-administrator tDCS Competency Checklist\\_1 5120](#)

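### Caregiver proficiency after remote training is assessed but never analysed, and the aborted-session count can look favourable while training fails

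*Combined protocol and SAP*

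**What the plan says.** The primary objective (Study objectives) is to "Demonstrate that remote tDCS sessions applied by a caregiver are feasible, complied and adhered to, and are safe in individuals with severe depression". Under Statistical Methods and Analysis, Primary, one sentence sets out how this is judged: "Feasibility and tolerability/safety will be evaluated using home-based data as it is collected by reported number of aborted sessions". It gives no denominator, no per-pair definition and no threshold.

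The section Home-use device and training to caregivers describes two earlier studies by the same team: "For all eight participant-pairs, the administrators, who ranged in age from 44 to 87, achieved proficiency by the third session of tDCS". It then says "The above studies utilize in-person training methods until the participant administrator achieves proficiency", and that for this trial "a video telemedicine-based training program is available to ensure minimal staff-participant contact". The same section reports that the equipment in a previously published home study "precluded some caregivers from achieving appropriate level of competency", and states that the present system overcomes those difficulties.

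The Visits section has caregivers supervised remotely until they are proficient without coaching. Its Week 1, Day 5 row lists a "Staff administered skills test for caregiver-administrators". The list of forms under Data storage and confidentiality includes a "Caregiver-administrator tDCS Competency Checklist" and a caregiver evaluation form. None of these appears in the analysis section.

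**The concern.** Feasibility here depends on a lay caregiver learning the procedure by video and then delivering it. A measure that counts only interrupted sessions does not show whether the caregiver learned it. Some training failures produce no interrupted session, because no session was started, because staff coached each one to completion, or because the pair left. Each such pair also takes its later sessions out of the pool in which aborts could occur.

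The study is meant to prepare a randomised trial of home-based tDCS. That trial would need to know what share of willing caregivers can be trained remotely. As written, the plan could report few aborted sessions without giving that share.

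**Working it through.** **1. What the count includes.** The device-block rules for the daily and taper sessions, after the Visits table, describe an aborted session as one started and then aborted. The notification paragraph just before them lists an aborted session separately from one not completed within the two-hour window. Training takes place inside the home sessions of Days 1 to 5. Therefore:

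| Course of the pair | Aborted sessions added |
|---|---|
| Training session started, then aborted | 1 each time |
| Eligible pair never starts a session | 0 |
| Sessions completed only under coaching, skills test not passed | 0 from those sessions |
| Caregiver withdraws | 0 from the sessions not held |

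**2. Evidence on training before this trial.** With 8 of 8 proficient, the exact (Clopper-Pearson) lower 95% limit is 0.025^(1/8) = 0.631, so the interval is 63.1% to 100%. All eight were trained in person. The documents give no figure for video training.

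**3. Sample size.** The Sample Size section gives 50, justified only by comparison with earlier studies. No precision target or feasibility threshold is stated, so the figure cannot be reproduced. I take it to mean 50 pairs.

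**4. How the count behaves.** Scheduled sessions per pair: 28 daily + 9 taper = 37. For 50 pairs: 50 × 37 = 1,850. Suppose k pairs never start and the others abort a fraction r of started sessions. Both k and r are assumptions.

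- Expected aborts = (50 − k) × 37 × r
- Undelivered share = [37k + (50 − k) × 37 × r] / 1,850

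| k (share of pairs) | Aborts, r = 2% | Undelivered, r = 2% | Aborts, r = 5% | Undelivered, r = 5% |
|---|---|---|---|---|
| 0 (0%) | 37.0 | 2.0% | 92.5 | 5.0% |
| 5 (10%) | 33.3 | 11.8% | 83.3 | 14.5% |
| 10 (20%) | 29.6 | 21.6% | 74.0 | 24.0% |
| 15 (30%) | 25.9 | 31.4% | 64.8 | 33.5% |

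At either abort rate the count falls as the number of non-starting pairs rises.

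**5. A second route.** Suppose 10 pairs complete five coached sessions with none aborted, do not pass the skills test, and leave. They add 0 aborted sessions. Undelivered sessions are 10 × (37 − 5) = 320, and 320 / 1,850 = 17.3%.

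**6. Precision of a per-pair proportion (exact 95% CI).**

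| Passed / pairs | Estimate | 95% CI |
|---|---|---|
| 50/50 | 100% | 92.9% to 100% |
| 45/50 | 90% | 78.2% to 96.7% |
| 40/50 | 80% | 66.3% to 90.0% |
| 35/50 | 70% | 55.4% to 82.1% |

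If 50 instead counts individuals, there would be 25 pairs, and 20/25 (80%) would give 59.3% to 93.2%.

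**The case against.** **Some training failures are counted.** A reader might infer that a caregiver who cannot be trained never registers as a failure. The documents do not support that, because training happens during real sessions and one that is started and aborted enters the count. The gap is limited to the routes in the table above.

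**Video training is not the only new element.** A reader might also infer that it is. The earlier pairs came from gait and balance and dementia studies with a 10-session course. This trial also changes the population, to medication-resistant depression, and the course, to 37 sessions.

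**The published home study is weak evidence of competency failure.** The protocol does not call it that study's main problem, gives no number of caregivers affected, and attributes it to sponge electrodes, elastic bands and a difficult interface. Its Background reports one withdrawal among 34 participants, for missed sessions, and 93% of scheduled sessions completed by the remaining 33. The present concern therefore rests on the change of training method and the definition of the count, not on that study.

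**The failures may be recoverable.** Sessions not completed in the window trigger an alert, completed sessions are monitored, reasons for withdrawal are documented, and more than 10 missed visits stops stimulation. No passage says that failing the skills test ends participation, so a pair that continues can still produce counted aborts. This stands as far as it goes. However, these provisions serve operations and stopping, and none is named as a feasibility result.

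**A completed-over-scheduled measure would catch non-starters and dropouts.** It would, if enrolled pairs formed the denominator. It still would not identify caregivers who complete sessions only with coaching.

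**Conclusion.** The concern holds in a limited form. Feasibility is judged by one count. The caregiver assessment that bears most directly on remote training is scheduled but has no place in the analysis. This is more than missing detail, because the stated measure can improve as training failure rises and so cannot by itself meet the primary objective.

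The direction follows from the definition of an aborted session, provided that the pairs concerned never start, complete only under coaching, or leave. The sizes are illustrative: the failure shares of 10% to 30%, the abort rates of 2% and 5%, and the reading of 50 as pairs are assumptions. The interval of 63% to 100% reflects only eight pairs with no failures observed, and is not evidence that remote training fails. The contents of the checklist and evaluation form are not shown, so they may already record a usable result. The point should be fixed, but it does not invalidate the study.

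**What to change.** In Statistical Methods and Analysis, Primary, add a feasibility outcome beside aborted sessions: the proportion of eligible, enrolled pairs whose caregiver passes the existing Day 5 skills test/competency checklist, with an exact 95% CI.

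- **Denominator.** Exclude screen failures. Consent is taken at the start of the screening call, before the health history and psychiatrist interview, so a denominator of all consented pairs would count patients found ineligible as training failures.
- **Failures.** Count as not passed any eligible pair that never starts, or that loses its caregiver before passing.
- **Pass criterion.** State it, including whether prompting is allowed. The Visits text describes proficiency as being without coaching, while the Day 5 row includes coaching.
- **Supporting results.** Report the session of first proficiency only if the existing checklist records it; the schedule shows a single test. Tabulate the caregiver evaluation form descriptively.

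The cost is a few sentences and a written pass definition. The assessment is already in the schedule, so no visit is added. The feasibility figure may look less favourable.

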At present, given the COVID-19 pandemic and the required and appropriate restrictions on individual mobility and outpatient medical encounters and procedures, access to rTMS, ECT, or similar in-clinic treatments is much more limited. These added difficulties to access ECT and rTMS are occurring at a time when the risk of mental health problems and of decompensation from pre-existing depression is extremely high due to the uncertainties, fears, and stressors caused by the COVID-19 pandemic and the social distancing. The risk of mood and mental health decompensation in the setting of social isolation and loneliness is particularly high among the elderly, who in turn are at a particularly high risk of serious complications of an infection with COVID-19 and thus are faced with particularly high stress, fears, and strict isolation regulations.

Therefore, the current COVID-19 pandemic makes the need for a safe, effective, home-based intervention for an acute, medication-resistant episode of uni- or bi-polar MDD particularly urgent. Transcranial direct current stimulation (tDCS) offers a suitable and readily available solution.

**Study design and purpose:** We propose a safety/feasibility study designed to determine whether it is possible for transcranial direct current stimulation (tDCS) interventions to be successfully delivered by a caregiver at the homes of adults who have medication-resistant MDD.

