## **Statistics**

## **Primary Analysis Plan for efficacy**

The primary outcome measure is the median percentage change (across study subjects) in s MADRS from baseline to 1 month follow up. The significance of changes will be assessed using the non-parametric Wilcoxon signed-rank test; however, since this is a pilot study to determine effect sizes, demonstration of a significant effect is not a defined goal of the study.

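### Feasibility, adherence and safety are the primary objective, but only MADRS change is called the primary outcome and given an analysis; the feasibility measure, aborted sessions, misses sessions never started

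*Combined protocol and SAP*

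**What the plan says.** Under *Study objectives*, the primary objective is: "Demonstrate that remote tDCS sessions applied by a caregiver are feasible, complied and adhered to, and are safe in individuals with severe depression". The secondary objective is: "Gather pilot data on the potential of home-based tDCS to induce clinically meaningful improvements in the severity of depression". The design statement at the end of *Purpose of the study*, whose sentence closes on the carer and the home setting, agrees with that order: "We propose a safety/feasibility study designed to determine whether it is possible for transcranial direct current stimulation (tDCS) interventions to be successfully delivered by a".

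Under *Statistical Methods and Analysis*, the subsection *Primary* begins with delivery: "Feasibility and tolerability/safety will be evaluated using home-based data as it is collected by reported number of aborted sessions". It then says that the primary outcome "will be change in the observer rated MADRS score from baseline to the 1-month follow-up", and defines response and remission on MADRS. QIDS-SR and Q-LES-Q-SF are the secondary outcomes, and CogState is an additional safety measure.

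The next section, *Primary Analysis Plan for efficacy*, restates the outcome: "The primary outcome measure is the median percentage change (across study subjects") in MADRS over the same interval. It names the only test in the plan: "The significance of changes will be assessed using the non-parametric Wilcoxon signed-rank test". It adds that, this being a pilot, "demonstration of a significant effect is not a defined goal of the study".

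**The concern.** The objectives and the outcomes rank the two questions differently, and nothing in the documents reconciles them. The label that usually carries a trial's headline is attached to the variable serving the secondary objective. The primary objective is left with one count that cannot answer it.

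Two things are at stake. First, the described design has no control arm and entry requires a MADRS of at least 20, so natural course and regression to the mean also push the change in the favourable direction. A report led by MADRS change could read well even if many pairs did not manage home delivery. Second, the stated purpose is to prepare a later randomized trial. That decision depends on whether caregivers can deliver the course, and the plan names no adherence outcome from which to conclude it.

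**Working it through.** **Step 1. The plan's own figure.** The sample size of 50 is justified only by comparison with published studies. No alpha, power, effect, SD, rate or dropout is given, so it cannot be reproduced for either MADRS or feasibility.

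**Step 2. Objectives against outcomes.**
- Feasibility, compliance and adherence (primary objective): measured by the number of aborted sessions. No denominator, adherence level, interval or test is given, and no completion outcome is listed.
- Safety (primary objective): the same aborted-session count, with CogState as an additional safety measure. Adverse events are recorded under *Adverse Events* but not named as an outcome.
- Depression severity (secondary objective): called the primary outcome in two places, with a summary statistic and a test.

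**Step 3. What the feasibility measure captures.** Scheduled sessions are 28 daily + 9 taper = 37 per pair. A session that is never started is not aborted. A pair that starts 15 sessions, aborts none and skips the other 22 has zero aborted sessions and has completed 15/37 = 41% of its schedule. The only numeric adherence rule, more than 10 missed visits under *Stimulation Stopping criteria*, stops an individual's stimulation; it is not a study-level criterion.

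**Step 4. Can MADRS look favourable when delivery is poor?**

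Inputs from the documents: n = 50, the signed-rank test, and the cited open-label home study's fall from 27.5 to 15.5, which is 12 points or 12/27.5 = 44%. Assumptions, because the documents give none: SD of change 8 to 12 points, normally distributed changes, two-sided 5%. The test was simulated on point changes, 1,500 runs per setting; the plan's summary is a percentage change, so this is an approximation.

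Main illustration: all 50 analysed, 20 with a mean fall of 12 points and 30 with a mean change of zero. The overall mean fall is 20 × 12/50 = 4.8 points.
- SD 8: power 0.93
- SD 10: power 0.81
- SD 12: power 0.68

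If the 20 who improve are the pairs who delivered the course, delivery is 20/50 = 40%. The exact 95% interval runs from the 2.5% quantile of Beta(20, 31) to the 97.5% quantile of Beta(21, 30): 26% to 55%.

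The answer depends on the scenario (SD 12 to SD 8):
- Only 20 supply data, all with the 12-point mean fall: 0.985 to above 0.999.
- Only 20 supply data, with a 4-point fall: about 0.27 to 0.57.
- All 50 analysed, 10 improve by 12 points and 40 do not change: 0.20 to 0.35.
- All 50 fall by 5 points for any reason: 0.79 to 0.98.

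**Step 5. Can 50 pairs support a feasibility primary outcome?** The exact interval for x of 50 is Beta(x, 51 − x) at 2.5% to Beta(x + 1, 50 − x) at 97.5%. For 40/50 this gives 80% (66% to 90%); for 45/50 it gives 90% (78% to 97%). The existing sample size gives a usable estimate.

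**The case against.** The best defence is that the labels are loose but the trial is not misdirected. Feasibility and tolerability come first under *Primary*. The heading *Primary Analysis Plan for efficacy* can be read as primary within efficacy. Delivery will also be observed: the text on daily sessions says staff are notified of sessions started, completed, aborted or not completed in the agreed window; adherence is monitored through completed sessions; caregivers take a skills test on Day 5; and the forms list includes a competency checklist, a side-effects questionnaire and evaluation forms. All of this stands. It means that delivery will be monitored, but not that any of these data are a named outcome with an analysis.

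A reader might infer that the trial's success or failure is to be read from MADRS. The documents do not support that: they define no success rule, and they say that a significant effect is not a goal. A reader might also infer that a favourable result is almost certain. The scenarios above do not support that either; power falls to 0.20 to 0.35 when only 10 of 50 improve. The near-certain figures need every contributing participant to share the full 12-point mean fall. Assessments are by phone, so pairs who stop stimulation might still be assessed, although the documents do not say so.

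**Conclusion.** The mismatch stands on the text. The primary objective concerns delivery and safety, while the only variable called the primary outcome, and the only one with an analysis, is MADRS change. Feasibility is not absent from *Primary*, but its one measure has no denominator or analysis and does not count sessions never started.

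The consequence is a misplaced headline, not a false declaration of success. In the main illustration, power of about 0.68 to 0.93 sits beside 40% delivery (95% CI 26% to 55%). Those power figures rest on the assumed SD of 8 to 12, two-sided 5%, and the chosen split of 20 improving and 30 unchanged. The mismatch itself depends on none of these.

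**What to change.** In *Statistical Methods and Analysis* and *Statistics*:

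- Name as primary outcome the per-pair proportion of the 37 scheduled sessions completed. Keep the denominator at 37, and count missed and aborted sessions as not completed.
- Report it over all enrolled pairs, with an exact 95% CI for the proportion of pairs meeting an adherence level that the sponsor chooses and writes down beforehand.
- Name adverse events as the accompanying safety outcome.
- Relabel MADRS change, response and remission as secondary (pilot efficacy) outcomes, and retitle *Primary Analysis Plan for efficacy* to match.
- State that the feasibility conclusion is drawn from the primary outcome whatever the MADRS result.

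Relabelling alone would not be enough, because a bare count of aborted sessions would still leave the primary objective without a usable outcome. The change should be made before results are seen, so that it cannot look like outcome switching.

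The cost is that MADRS loses its primary label, the sponsor must commit to an adherence level, and a little more analysis is needed. Session completion is already captured electronically and the sample size need not change.
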